8.4.3 GOS-E at Three and Six Months Post-injury

The extended GOS is an 8-point scale with the following categories: Dead, Vegetative State, Lower Severe Disability, Upper Severe Disability, Lower Moderate Disability, Upper Moderate Disability, Lower Good Recovery, and Upper Good Recovery.

The null hypothesis that the global assessment of outcome, as measured by the GOS-E at 3 or 6 months, is the same in each treatment group will be tested using the 2-sided Wilcoxon Rank-Sum test, which can be obtained from the NPAR1WAY procedure in SAS®.

A two-sided, 5% significance level will be used to test the null hypothesis. If rejected at the 5% level ($p < 0.05$), it will be concluded that there is a statistically significant difference in the global assessment of outcome between the 2 treatment groups, as measured by the GOS-E. The

magnitude of the summary statistics will be examined to determine the direction of the treatment difference.

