9 STATISTICAL METHODS

All analyses and reporting of study results will be conducted using SAS V9.1.3 In addition EAST will be used to adjust for the interim analysis.

All variables will be presented using appropriate descriptive statistics according to the variable nature:

- Continuous variables: number of non-missing observations, mean, standard deviation , minimum, first quartile (Q1), median, third quartile (Q3), maximum,
- Categorical variables: number of non-missing observations, absolute and relative frequency (n and percentages (%)),
- Time-to-event variables: number of non-missing observations, number and percentage of censored observations, first quartile, median (and 95% CI), third quartile, and Kaplan-Meier survival curves.

The behavior over time of continuous variables will be analyzed by presenting descriptive statistics for each time point and the difference compared to baseline (actual values and change from baseline). The behavior over time of categorical data will be analyzed by presenting the descriptive statistics for each time point and the shift compared to baseline.

The decimal places for summary statistics and percentages will be as follows:

- Precision of data + 2 decimal places (dp) for standard deviations,
- Precision of data + 1 dp for means, medians and quartiles,
- Same precision as data for minimum and maximum,
- 1 dp for percentages except when the percentage is 100% in which case no dp would be presented, and

The primary and confirmatory efficacy analyses will be 2-sided and conducted at a 1% significance level. All secondary efficacy tests will be 2-sided and conducted at a 5% significance level.

The randomization will be stratified by region. This variable will be included as a covariate in the primary and secondary GOS efficacy analyses.

Secondary efficacy analyses will be conducted in ranked order as listed in Section 9.5.2 with the understanding that no confirmatory claims can be based on variables that have a rank lower than or equal to that variable whose null hypothesis was the first that could not be rejected at the $p<0.05$ significance level.

All exploratory analyses will be considered supportive in nature, and therefore no adjustment will be made for multiple testing of exploratory variables.

All data will be included in subject data listings for all subjects in the mITT population.

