If the p-value from the test of the null hypothesis of $\beta_1 = 0$ is less than 0.0003 (at the interim) or 0.0098 (at the final analysis), it will be concluded that BHR-100 is statistically significantly different from placebo with respect to the GOS at 6 months following injury. The odds of some degree of improvement in the GOS at 6 months will be modeled and the corresponding common odds ratio for treatment, e^{β_1} , can then be interpreted to determine the direction of the treatment difference as follows. With the placebo group being considered as the reference category, if the odds ratio (OR_{BHR-100/placebo}) is greater than 1, the odds of some improvement in the GOS at 6 months is greater in the BHR-100 treatment group compared to placebo.

In the event that the primary efficacy analysis does not show statistical significance at the study-wise 1% significance level, please refer to section 9.5.1.4 for further details on how the statistical significance of the primary efficacy analysis should be interpreted.

The POM will be fitted in SAS[®] using the PROC LOGISTIC procedure.

Goodness of fit of the model will be assessed using the Deviance and Pearson tests (add SCALE = NONE AGGREGATE to the MODEL statement of PROC LOGISTIC) to compare the fitted model with the saturated model. If these tests are not statistically significant it implies that the model fits the data adequately.

The score test for the proportional odds assumption and individual p-values associated with the tests of effects (treatment, geographic region, age, GCS motor score, pupil response, and CT classification) will be summarized for the POM of GOS at 6 months post injury.

The odds ratios and associated 95% CIs for the levels of the effects relative to a reference category will be presented for all factors and covariates included in the POM of GOS at 6 months post injury.

In addition to the results of the hypothesis tests from the statistical modeling, the number of non-missing observations, absolute and relative frequency (n and percentages), will be provided by treatment group for the GOS categories at 6 months post injury.

The analyses above will be repeated for the straight observed case analysis (no imputation of 6-month GOS or covariates) in the mITT population, the straight observed case analysis in the PP population (no imputation of 6-month GOS or covariates), and the analysis of imputed missing values in the mITT population for US subjects only.

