9.5.1.3 Sensitivity Analysis (Dichotomized Model)

The GOS at 6 months post injury will be dichotomized into Good Recovery, Moderate Disability versus Severe Disability, Vegetative Status/Dead. As a supportive analysis, the binary outcome will be analyzed using logistic regression analysis. The logistic regression model will be fitted including the effect of treatment, geographic region (North America, Europe, Asia, and South America), age, GCS motor score, pupil response, and CT classification.

If $Y = \text{response} = \text{GOS at 6 months following injury}$.

Model

$Y_1 = 0$ (not event), if $Y = \text{vegetative state or dead, severe disability}$
 $Y_1 = 1$ (event), if $Y = \text{moderate disability, good recovery}$

The dichotomous logistic regression model can be expressed as follows:

$$\ln(P/(1 - P)) = \alpha_0 + \beta_1 X_1 + \beta_2 X_2 + \beta_3 X_3 + \beta_4 X_4 + \beta_5 X_5 + \beta_6 X_6,$$

where

- \ln is the natural logarithm,
- P = Probability of an ‘event’ (moderate disability, good recovery) = Probability that $Y = 1$,
- $P/(1 - P)$ = odds of an ‘event’,
- X_1 = treatment group,
- β_1 = effect of treatment,
- X_2 = region,
- β_2 = effect of region,
- X_3 = age,
- β_3 = effect of age,
- X_4 = GCS motor score,
- β_4 = effect of GCS motor score,
- X_5 = pupil response,
- β_5 = effect of pupil response, and
- X_6 = CT classification,
- β_6 = effect of CT classification.

The logistic regression model will be used to test the null hypothesis that the odds of an ‘event’, i.e. observing a response of moderate disability or good recovery on the outcome variable, GOS at 6 months following injury, adjusted for region, age, GCS motor score, pupil response, and CT classification is the same in both treatment groups, i.e.

Null Hypothesis: $H_0: \beta_1 = 0$
Alternative Hypothesis: $H_1: \beta_1 \neq 0$

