If the p-value from the test of the null hypothesis of $\beta_1 = 0$ is less than 0.05, it will be concluded that BHR-100 is statistically significantly different from placebo with respect to the GOS at 6 months following injury. The odds of an 'event' (moderate disability or good recovery) in the GOS at 6 months will be modeled and the corresponding common odds ratio for treatment, e^{β_1} , can then be interpreted to determine the direction of the treatment difference as follows. With the placebo group being considered as the reference category, if the odds ratio ($OR_{BHR-100/placebo}$) is greater than 1, the odds of a favorable outcome in the GOS at 6 months is greater in the BHR-100 treatment group compared to placebo.

The logistic regression analysis will be fitted in SAS[®] using the PROC LOGISTIC procedure.

Goodness of fit of the model will be assessed as outlined above for the Proportional Odds Model.

The individual p-values associated with the tests of effects (treatment, geographic region, age, GCS motor score, pupil response, and CT classification) will be summarized for the Logistic Regression Model of GOS at 6 months post injury.

The odds ratios and associated 95% CIs for the levels of effects relative to a reference category will be presented for all factors and covariates included in the Logistic Regression Model of GOS at 6 months post injury.

In addition to the results of the hypothesis tests from the statistical modeling, the number of non-missing observations, absolute and relative frequency (n and percentages), will be provided by treatment group for the dichotomized GOS categories at 6 months post injury.

The primary dichotomized analysis will be based on missing values of 6-month GOS and covariates imputed. It will also be repeated for the straight observed case analysis (no imputation of 6-month GOS or covariates) in the mITT population and the straight observed case analysis in the PP population.

A bar chart illustrating the percentage of responses in each of the dichotomized categories for each treatment group will be produced for the GOS at 6 months (observed values and missing values imputed) for the mITT population.

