9.5.1.4 Interpretation of Statistical Significance of Primary Efficacy Analysis

In the event that the primary efficacy analysis does not show statistical significance at the study-wise 1% significance level, i.e. the final analysis p-value is not less than 0.0098, a final adjusted p-value will be calculated and the result considered statistically significant at the 5% level if the adjusted p-value is less than 0.05. The adjusted p-value will be calculated using EAST (Cytel Statistical Software, Cambridge, MA) or other appropriate statistical software

package to adjust for the interim analysis using the pre-specified boundaries discussed above and in section 7.

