9.5.2 Secondary Variables

Secondary efficacy parameters will be ranked as follows:

- 1) GOS-E at Month 6,
- 2) Mortality at Month 6 in mITT population (comparison of incidence of death),
- 3) GOS at Month 3,
- 4) GOS-E at Month 3,
- 5) Mortality at Month 1 in mTT population (comparison of incidence of death),
- 6) SF-36 mental composite score at Month 6,
- 7) SF-36 physical composite score at Month 6
- 8) SF-36 mental composite score at Month 3, and
- 9) SF-36 physical composite score at Month 3.

No confirmatory claims can be based on variables that have a rank lower than or equal to the variable whose null hypothesis was the first that could not be rejected at the p<0.05 significance level.

9.5.2.1 Mortality at Month 1, Month 6

These efficacy variables are obtained by collecting the survival status from the date of injury (Day 1 of the study) until Day 30 (Month 1) and Day 180 (Month 6) respectively as lost to follow-up, consent withdrawn, alive, dead or other. Every effort will be made to ascertain the survival status of subjects with status other than dead or alive, but in the absence of further information these observations will be omitted from the analysis. The 1-month mortality rate will be defined as the proportion of subjects at risk in the mITT population (subjects for whom the survival status at Day 30 is known) who died on or before Study Day 30. Similarly, the 6-month mortality rate will be defined as the proportion of subjects at risk in the mITT population who died on or before Study Day 180.

The hypothesis that the mortality rate observed in each treatment group is the same will be tested using the Fisher's Exact test.

$$\begin{array}{ll} \text{Null Hypothesis:} & H_0: p_1 = p_2 \\ \text{Alternative Hypothesis:} & H_1: p_1 \neq p_2 \end{array}$$

where p_1 = proportion of deaths in the BHR-100 treated group and p_2 = proportion of deaths in the placebo treated group.

A 2-sided, 5% significance level will be used to test the null hypothesis. If rejected ($p < 0.05$), it will be concluded that there is a statistically significant difference in the proportion of deaths between the 2 treatment groups.

In addition to the formal inference testing discussed above, 2-sided 95% confidence intervals for the difference in the proportion of deaths between BHR-100 and placebo treatment groups will be calculated.

Summaries of mortality at Months 1 and 6 will be presented for both the mITT and PP populations.

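### A supportive model can declare the primary endpoint significant at an unadjusted 0.05, and claims on the ranked secondaries are not tied to the primary

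*SAP*

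**What the plan says.** The primary test is the proportional odds model for Month 6 GOS. Under SAP 9.5.1.1 its p-value must be below 0.0003 at the interim or below "0.0098 (at the final analysis), it will be concluded that BHR-100 is statistically significantly different from placebo with respect to the GOS at 6 months". If it misses, SAP 9.5.1.4 provides a second tier: "the result considered statistically significant at the 5% level if the adjusted p-value is less than 0.05".

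SAP 9.5.1.3 then fits a logistic model to good recovery or moderate disability against the rest. It describes the model's role this way: "As a supportive analysis, the binary outcome will be analyzed using logistic regression analysis". Its decision rule is nevertheless that if the p-value "is less than 0.05, it will be concluded that BHR-100 is statistically significantly different from placebo with respect to the GOS at 6 months". Protocol 8.3.2 carries the same sentence at the same threshold.

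For the secondaries, SAP 9 states: "All secondary efficacy tests will be 2-sided and conducted at a 5% significance level". It continues: "Secondary efficacy analyses will be conducted in ranked order as listed in Section 9.5.2 with the understanding that no confirmatory claims can be based", with the bar running from the first failed variable downward. SAP 9.5.2 repeats the rule: "No confirmatory claims can be based on variables that have a rank lower than or equal to the variable whose null hypothesis was the first" not rejected at 0.05. The list of nine starts with GOS-E at Month 6, and the primary is not in it. Protocol 8.4.3 says of a GOS-E result below 0.05 that "it will be concluded that there is a statistically significant difference in the global assessment of outcome between the 2 treatment groups", with no condition attached.

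**The concern.** There are two faults.

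**(a) Two rules for one conclusion.** The conclusion in SAP 9.5.1.3 is about Month 6 GOS, the primary endpoint, and is worded as the primary's own. It needs only 0.05, is not linked to the primary result, and still applies when the 5% tier of 9.5.1.4 has failed. A study report that followed the plan could call the primary endpoint both not significant and significantly different, each under a prespecified rule.

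**(b) A gate without the primary.** The ranking stops only when a secondary fails. Nothing bars a confirmatory claim on GOS-E after the primary has failed. GOS-E grades the same outcome more finely, so such a claim would not be independent support.

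SAP 1 says this version serves the clinical study report and a potential marketing application, where it matters which results count as claims.

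**Working it through.** **Inputs.** Placebo Month 6 GOS is 31% good recovery, 21% moderate disability, 19% severe disability and 29% vegetative or dead (SAP 3.1). N is 1180, allocated 1:1, with OR 1.5, 90% power and two-sided alpha 0.01 (SAP 3.1). The interim is at 400, with thresholds 0.0003 and 0.0098 (SAP 7, Table 2). The dichotomised model and the secondaries are tested at 0.05.

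**1. The plan's own figures.** Whitehead's formula is N = 12(z₁₋α/₂ + z_power)² / [ln(OR)² (1 − Σp̄³)]. At OR 1.5 the treated distribution is 40.3/21.7/16.7/21.4%, so 1 − Σp̄³ = 0.9234. Then N = 12 × (2.576 + 1.282)² / (0.4055² × 0.9234) ≈ 1176, against 1180 stated. For the two looks, with correlation √(400/1180) = 0.58, critical values 3.65 and 2.58 give a cumulative error of 0.01005 (Table 2: 0.0101). The thresholds 0.0003 and 0.0098 give 0.0100. The fallback at an adjusted 5% corresponds to a final |z| above 1.961.

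**2. How closely the tests agree.** With no effect, the proportional odds score test uses midrank scores 0.155, 0.415, 0.615 and 0.855 (variance 0.0775). The dichotomy scores 1, 1, 0, 0 (variance 0.52 × 0.48 = 0.2496). Their covariance has size |0.1352 − 0.5 × 0.52| = 0.1248. The correlation is 0.1248 / √(0.0775 × 0.2496) = 0.897. For the 7-level GOS-E the correlation with the primary is 0.982–0.985, depending on how each GOS level splits (30:70 to 70:30 assumed).

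**3. False conclusions with no effect.** In 400,000 simulated trials the primary succeeds in 1.00% and the dichotomised test in 5.04%. The dichotomised test succeeds while the primary misses its 1% boundary in 4.16%, so either succeeds in 1.00 + 4.16 = 5.16%. With the 5% tier the primary succeeds in 4.97%. The dichotomised test succeeds after that tier fails in 2.12%, so either succeeds in 4.97 + 2.12 = 7.09%. That 2.12% is 2.12/5.04 = 42% of the trials in which the dichotomised rule is met.

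| Results counted | Primary at 1% | Primary with 5% tier |
|---|---|---|
| Primary alone | 1.0% | 5.0% |
| Primary or dichotomised | 5.1–5.2% | 7.1–7.4% |
| Primary or Month 6 GOS-E | 5.0% | 5.8–6.2% |
| Any of the three | 7.2–7.6% | 7.7–8.3% |

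The lower ends use the correlations in step 2, without covariates. The upper ends use a normal model with lower correlations to allow for covariate adjustment: 0.86 (primary–dichotomised), 0.97 (primary–GOS-E) and 0.835 (dichotomised–GOS-E). These are assumptions. Across both sets, the dichotomised rule is met after the primary misses 1% in 4.1–4.2% of null trials, and after both tiers fail in 2.1–2.4%.

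**4. Which rule is easier to meet.** At OR 1.27 the dichotomised test at 0.05 has 53% power, against 38% for the primary at its final boundary. At OR 1.5 the figures are 93% and 90%. The supportive rule is the easier one in both cases.

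**The case against.** The best defence is that the SAP, read as a whole, settles the primary's status in one place. The dichotomised model has its own null hypothesis and sits under a sensitivity heading. SAP 9.5.1.1 sends a missed primary only to 9.5.1.4, which gives that model no role. The concluding phrase is stock wording that also appears for mortality and SF-36, so it need not be a claim. On the secondaries, the ranking only forbids claims and never grants one, and many readers would assume the primary comes first.

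Part of this limits the size of the point:

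- The fallback to 5% is disclosed, so 5.0% is the fairer baseline. Against it the dichotomised rule adds 2.1–2.4 points, GOS-E adds 0.8–1.2, and both add 2.7–3.3.
- No interim inflation is shown. The dichotomised test is taken here at the final analysis only, and SAP Appendix 2 marks its summary table for the DSMB but not its test.
- The fixed sequence does control error at 5% within the secondary family.
- Part (b) is an omission. The plan does not say that claims survive a failed primary.
- SAP 1.1 replaces the GOS-E test in Protocol 8.4.3, so that section is weaker evidence.

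It does not remove the fault. The sentence in 9.5.1.3 and 8.3.2 names Month 6 GOS, the endpoint itself, and sets a threshold for concluding on it. A supportive label does not cancel a stated decision rule. An assumed gate would also leave open which of the two primary tiers opens it.

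**Conclusion.** The point holds on both parts. As written, the supportive model concludes on the primary endpoint at 0.05 independently of the primary, and the rule for confirmatory secondary claims omits the primary. With no effect on any endpoint, the chance of at least one such result is 7.2–7.6% against the 1% boundary, or 7.7–8.3% against 5.0% once the disclosed fallback is counted. In 2.1–2.4% of null trials the dichotomised rule declares a difference after both primary tiers have failed.

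The ranges rest on assumed GOS-E splits and covariate effects. The splits move the any-of-three figure in the 1% column by under 0.1 point. The contradiction between the rules does not depend on either assumption. The two-look primary test and the 5% tier are not in question. This should be fixed before database lock.

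**What to change.** 1. In SAP 9.5.1.3 and Protocol 8.3.2, delete the sentence that draws a conclusion at 0.05. Report the dichotomised odds ratio and confidence interval as supportive only.
2. In SAP 9 and 9.5.2, state that confirmatory claims on the ranked secondaries require a significant primary. If 0.0003 or 0.0098 is met, the ranking proceeds at 5% per variable as now. If only the adjusted 0.05 is met, any secondary claim is labelled as belonging to that tier. If neither is met, the secondaries are descriptive. This also governs the concluding phrases left in the mortality, GOS-E and SF-36 sections.

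With no effect on any endpoint, the chance of a claim returns to 1.0% in the 1% tier and 5.0% over both tiers. The gate does not change the 5% risk on a null secondary once a real primary effect has opened it.

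No new data or analyses are needed, and N stays at 1180. The change can be listed in SAP 1.1. That section shows that the change of analysis population went through a Special Protocol Assessment modification, so the change to Protocol 8.3.2 may need regulatory notification.

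The price is some lost true claims. With the two-tier gate, a Month 6 GOS-E claim at OR 1.5 falls from 97.6% to 96.8% of trials (89.8% in the 1% tier). At OR 1.27 it falls from 64.2% to 60.4% (38.1% in the 1% tier). These figures assume proportional odds and no covariates. The cost for mortality, or under non-proportional effects, was not worked out.

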9.5.1.4 Interpretation of Statistical Significance of Primary Efficacy Analysis

In the event that the primary efficacy analysis does not show statistical significance at the study-wise 1% significance level, i.e. the final analysis p-value is not less than 0.0098, a final adjusted p-value will be calculated and the result considered statistically significant at the 5% level if the adjusted p-value is less than 0.05. The adjusted p-value will be calculated using EAST (Cytel Statistical Software, Cambridge, MA) or other appropriate statistical software

package to adjust for the interim analysis using the pre-specified boundaries discussed above and in section 7.

9.5.1.5 Handling of Missing Data

Please refer to section 5 for further details on the handling of missing data.

9.5.1.6 Exploratory Analysis

An exploratory analysis will be conducted to assess each of the following covariates of interest: treatment (BHR-100 vs. placebo), region (North America vs. Europe vs. Asia vs. South America), age, race (white vs. non-white), GCS motor score (1-2 vs. 3 vs. 4 vs. 5-6), pupil response (bilateral vs. unilateral/no reactive pupils/not testable), CT classification (I/II vs. III vs. IV vs. V/VI), presence of hypoxia (yes/suspected vs. no/unknown), presence of hypotension (yes/suspected vs. no/unknown), presence of traumatic subarachnoid hemorrhage (yes vs. no), gender (male vs. female), and time to first dose of study medication from TBI (0-4 vs. 4-6 vs. 4-8 vs. >8 hours), for inclusion into an expanded model. Each covariate, along with the corresponding interaction with treatment term, will be included in a simple model with treatment. A backward selection model will be fit beginning with all covariates. Factor by treatment interactions will be included in the backward elimination model if the p-value<0.10 in the corresponding simple model. A significance level of 0.05 may be too stringent and may exclude important variables from the model, so a significance level of 0.1 will be used for the backward selection process. If the interaction term is significant, an exploratory subgroup analysis will be performed for the corresponding covariate.

This analysis will be conducted for the POM based on imputation of missing data. Missing covariates will not be imputed for the exploratory analysis.

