9.6 Safety Analyses

9.6.1 Adverse Events

For this study, it is intended to limit the collection of AEs to the window in which events are considered treatment-emergent. Treatment-emergent adverse events (TEAEs) are defined as events that start on or after the first dose of study medication and up to 15 days and 6 months after the initiation of study treatment, for AEs and SAEs respectively.

Partial start dates of AEs will be imputed in order to determine whether or not the AE is TE. If just the day is missing, and any date of dose administered is within the month of the AE, the AE will be treated as TE. If the month is missing and the year is present, and any date of dose administered is within the year of the AE, the AE will be treated as TE. If the year is missing,

the AE will be treated as TE. For the imputation, the day will be set to the first date of that month, or the first dose date, if the first dose date is within that month. Alternatively, if the month is missing the month will be set to January, or the first dose date, if the first dose date is within that year.

AEs will be coded using the MedDRA international thesaurus version 13.0 with no updates, adding system organ class (SOC) and preferred term. The AE summaries will be presented for TEAEs only. The total number of subjects reporting at least one AE and the number of AEs will be summarized by treatment group. The initial summary will also provide a breakdown of events that:

- Are treatment-related,
- Are serious,
- Are treatment-related and serious,
- Resulted in the study drug being prematurely discontinued,
- Are treatment-related and resulted in the study drug being prematurely discontinued,
- Resulted in death, and
- Are treatment-related and resulted in death.

Additionally, the overall summary of AEs will be summarized by treatment group for the subgroups of interest: gender, race group (white vs. non-white vs. not allowed to obtain), and age group (≤ 45 years vs. > 45 years).

The number and percentage of subjects with at least one TEAE and the number of TEAEs will be presented by SOC, preferred term, and treatment group for the following summaries:

- All AEs,
- All AEs by gender,
- All AEs by race group,
- All AEs by age group,
- Treatment-related AEs,
- All AEs, by maximum severity,
- Treatment-related AEs, by maximum severity,
- All AEs, by maximum relationship,
- All AEs that resulted in the study drug being prematurely discontinued, and

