Table 14.2.3.12 Analysis of Dichotomized (GR, MD, SD vs. V/D) Glasgow Outcome Scale¹ at 6 Months Post Injury - Missing Values Imputed (mITT Population)

Table 14.2.3.13 ORs¹ and 95% CIs² for Dichotomized (GR, MD, SD vs. V/D) Glasgow Outcome Scale at 6 Months Post Injury - Missing Values Imputed (mITT Population)

Table 14.2.4.1 Analysis of Glasgow Outcome Scale¹ at 6 Months Post Injury - Exploratory Analysis - Missing Values Imputed (mITT Population) - **EXAMPLE SHELL***

Effect	DF ⁴	Wald Chi-Square ⁵	P-Value ⁵	Interaction Wald Chi-Square ⁵	Interaction with Treatment P-value
Simple Model²					
Treatment	xx	xx.xxx	x.xxx	xx.xxx	
Region	xx	xx.xxx	x.xxx	xx.xxx	x.xxx
Age	xx	xx.xxx	x.xxx	xx.xxx	x.xxx
Race	xx	xx.xxx	x.xxx	xx.xxx	x.xxx
GCS Motor Score	xx	xx.xxx	x.xxx	xx.xxx	x.xxx
Pupil Response	xx	xx.xxx	x.xxx	xx.xxx	x.xxx
CT Classification	xx	xx.xxx	x.xxx	xx.xxx	x.xxx
Hypoxia	xx	xx.xxx	x.xxx	xx.xxx	x.xxx
Hypotension	xx	xx.xxx	x.xxx	xx.xxx	x.xxx
Subarachnoid Hemorrhage	xx	xx.xxx	x.xxx	xx.xxx	x.xxx
Gender	xx	xx.xxx	x.xxx	xx.xxx	x.xxx
Time to first dose	xx	xx.xxx	x.xxx	xx.xxx	x.xxx
Backward Elimination Model³					
Treatment	xx	xx.xxx	x.xxx		
Region	xx	xx.xxx	x.xxx		
Age	xx	xx.xxx	x.xxx		
...					

¹ Response variable Glasgow Outcome Scale at 6 months post injury has 4 values (Good Recovery, Moderate Disability, Severe Disability and Vegetative State/Dead).

² Each factor is included in a model with treatment and the factor by treatment interaction and run individually.

³ The backward elimination model begins with all factors in the model. Factor by treatment interactions with p<0.10 in the simple model are included in the Backward Elimination Model. Factors must have a significance level of p<0.10 to remain in the model. Only the final model is shown.

⁴ DF=Degrees of Freedom.

⁵ The Type 3 analysis of effects are based on the Wald Chi-Square test.

Source: Listing 16.2.6.1.4 and 16.2.6.1.6.

Program: xxxxxxx.sas, Output: xxxxxxx.rtf, Generated on: DDMONYYYY xx:xx, Page x of x

[* The above template is an example. ONLY the final exploratory model will be presented, so not all the terms indicated above may be included.]

If any of the interaction terms in the exploratory analysis are significant, the following subgroup analyses will be presented:

Table 14.2.4.2 Analysis of Glasgow Outcome Scale¹ at 6 Months Post Injury by Region - Proportional Odds Model - Missing Values Imputed (mITT Population)

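### The exploratory expanded model can drop treatment, gives unobtainable race no level, and has two different rules for showing subgroup tables

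*SAP*

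**What the plan says.** SAP 9.5.1.6 names the candidates for an expanded model of 6-month GOS, starting with "treatment (BHR-100 vs. placebo), region (North America vs. Europe vs. Asia vs. South America), age, race (white vs. non-white" and continuing through motor score, pupils, CT class, hypoxia, hypotension, subarachnoid hemorrhage, gender and time to first dose. That is treatment plus 11 other factors. Each factor is first fitted in a simple model with treatment and their interaction. Then "A backward selection model will be fit beginning with all covariates", with interactions added if they reached p<0.10 in the simple model, and "a significance level of 0.1 will be used for the backward selection process". On missing data: "Missing covariates will not be imputed for the exploratory analysis".

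Footnote 3 to the Table 14.2.4.1 shell (Appendix 3) adds: "Factors must have a significance level of p<0.10 to remain in the model. Only the final model is shown". A note under the shell warns that some listed terms may be absent.

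On race, the adverse event subgroups in SAP 9.6.1 use "race group (white vs. non-white vs. not allowed to obtain", and the demographics shell (Table 14.1.4.1) has the same separate category.

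On subgroups, 9.5.1.6 calls for a subgroup analysis of the covariate whose interaction is significant, without giving the level. Appendix 3 says: "If any of the interaction terms in the exploratory analysis are significant, the following subgroup analyses will be presented", and then lists Tables 14.2.4.2 to 14.2.4.23, two for each of the 11 factors.

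**The concern.** There are three gaps in one short section. First, treatment is treated like any other candidate, so the selection rule can remove the one term a reader of a treatment trial will look for. It is most likely to be removed when the effect is nil or modest.

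Second, the same list gives a level to unknown hypoxia and hypotension and to untestable pupils, but gives none to race that may not be obtained. In an unimputed model that starts with race, a subject without a race level is lost at the first step. Unless the data set is rebuilt after each removal, that subject stays lost even if race is later dropped.

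Third, two programmers could follow the SAP and produce different sets of subgroup tables. The choice would be made after the interaction p-values are known.

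**Working it through.** **Reproducing the plan's sample size.** The inputs are in SAP 3.1: placebo GOS 31/21/19/29%, common odds ratio 1.5, two-sided alpha 0.01, power 90%, total 1180. Whitehead's formula is N = 12(z₁+z₂)² / [(ln OR)² × S], with S = 1 − Σp̄³ and p̄ the mean of the two arms' category proportions. At OR 1.5, p̄ is 0.356, 0.213, 0.178 and 0.252, so S = 0.923. Then N = 12 × (2.576+1.282)² / (0.1644 × 0.923) ≈ 1176, against 1180 stated. The same variance gives final-analysis power at 0.0098 of 38.2% (OR 1.27) and 90.0% (OR 1.5), against 39.36% and 90.66% in SAP Table 3. The approximation is good enough for what follows.

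**Chance that treatment fails the 0.10 stay rule.** SE(ln OR) = √[12/(N×S)] = 0.105 at N=1180. With δ = ln OR / SE, the chance of p≥0.10 is Φ(1.645−δ) − Φ(−1.645−δ).

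| True OR | ln OR | δ | Chance of removal |
|---|---|---|---|
| 1.0 | 0 | 0 | 90% |
| 1.1 | 0.095 | 0.91 | 76% |
| 1.2 | 0.182 | 1.74 | 46% |
| 1.27 | 0.239 | 2.28 | 26% |
| 1.5 | 0.405 | 3.86 | 1.3% |

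These figures use an unadjusted standard error, the full 1180 subjects, and no retained treatment interaction.

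**Race.** The documents give no rate for race not obtainable, so the share q is an assumption. Subjects lost are 1180q, and the standard error rises by the factor 1/√(1−q).

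| Assumed q | Lost | Kept | SE increase | Removal chance at OR 1.27 |
|---|---|---|---|---|
| 5% | 59 | 1121 | 3% | 28% |
| 10% | 118 | 1062 | 5% | 30% |
| 20% | 236 | 944 | 12% | 35% |
| 30% | 354 | 826 | 20% | 40% |

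The loss affects the backward model and the simple model for race, not the other ten simple models.

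**Subgroups, the two rules side by side.** If only the region interaction is significant, 9.5.1.6 yields the two region tables. Appendix 3, read literally, yields all 22. Appendix 2 lists all 22 with no condition.

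As to how well an interaction test works as a gate, take a true ratio of odds ratios of 1.5 between two equal halves. The standard error of the interaction is 2 × 0.105 = 0.209, so δ = 0.405/0.209 = 1.94. Power is about 61% at 0.10 and 49% at 0.05. A real difference of that size would often not open the gate.

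**The case against.** The strongest answer is that little depends on this model. SAP section 9 calls exploratory analyses supportive. A reader might infer that the trial could end without an adjusted treatment odds ratio. It could not: the primary model always contains treatment and reports its odds ratio and 95% CI (Table 14.2.1.3), and it is repeated for observed cases, the per-protocol set, US subjects and without covariates. Every simple model in 9.5.1.6 also contains treatment. Nor does the SAP say that the expanded model is meant to check the primary result. If a treatment interaction is retained and the software enforces hierarchy, treatment would stay. All of this stands and limits the point, but the SAP states no hierarchy rule.

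On race, no section says how unobtainable values are coded in this model, and an unwritten rule may exist. The loss of these subjects is therefore a strong inference from the three-way grouping elsewhere, not a stated fact. A reader might go further and suppose that whole countries disappear. The documents name no country where race cannot be recorded, so that is unsupported.

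On subgroups, a reader might infer that only results picked for a small p-value will ever be seen. The simple-model block of Table 14.2.4.1 already carries an interaction p-value for each of the 11 factors, although the looser note beneath it, that only the final model is presented, sits awkwardly with that. US-only and prognosis-group results are unconditional. With 11 independent null interactions, the chance of at least one at p<0.10 is 1 − 0.9¹¹ = 69%. That measures multiplicity at screening; it is not the chance that a misleading table appears, and showing more tables does not reduce it.

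**Conclusion.** The point holds for the exploratory expanded model only. That treatment can be eliminated follows directly from the wording of 9.5.1.6 and the Table 14.2.4.1 footnote. The chance runs from about 90% at no effect to about 1% at the design odds ratio, and covariate adjustment or a retained interaction would change these figures. The loss of subjects with unobtainable race is likely but inferred, and its size cannot be known from the documents; 5% to 30% is an assumed range. The subgroup issue is a conflict between 9.5.1.6 and Appendix 3, with the significance level left open. No confirmatory conclusion is at risk, because the primary model keeps treatment and does not use race. It is still worth correcting, because the remedy is simple and an expanded model without a treatment estimate is of little use to a reader.

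**What to change.** In SAP 9.5.1.6 and the Table 14.2.4.1 shell:

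- State that treatment is forced into every step, and report its odds ratio and 95% CI from the final model. The shell now has only degrees of freedom, chi-square and p-value columns, with odds ratios left to the SAS output appendix.
- Code race as white, non-white or not allowed to obtain, as the adverse event tables do, or leave race out of the multivariable model.
- Make 9.5.1.6 and Appendix 3 give one subgroup rule. Preferably produce the already titled tables for all 11 factors whatever the interaction result, beside the interaction p-values. If a gate is kept, state its level.
- Before those tables can be run, define the age groups for efficacy (a cut at 45 years appears only for adverse events) and correct the time-to-first-dose bands, which overlap as written (4-6 and 4-8 hours).

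Forcing treatment in makes its chance of removal zero, and a third race level keeps all 1180 subjects as far as race is concerned. The cost is SAP wording, two definitions, extra runs of tables already listed, and somewhat more exploratory output to read with caution.
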